**BACKGROUND AND SIGNIFICANCE**

Diabetic ketoacidosis (DKA) is an acute, life-threatening complication of diabetes which requires treatment with intravenous (IV) fluid and insulin to correct hyperglycemia and reverse acidosis. Current DKA management guidelines recommend normal saline (0.9% sodium chloride) for resuscitation and treatment. However, saline's chloride content is higher than that of human plasma and can cause a hyperchloremic metabolic acidosis, particularly when administered in large volumes (often needed in patients with DKA). Use of saline may thus worsen the clinical condition of patients who are already in an acidotic state. Alternatives to saline are balanced crystalloids (e.g. Ringer's lactate-RL) which have chloride concentrations similar to human plasma; therefore, treatment with balanced crystalloids may lead to faster DKA resolution. One recent study (Self et al.) of emergency department (ED) patients presenting with DKA demonstrated that treatment with balanced crystalloids resulted in more rapid DKA resolution compared to saline (13.0 vs 16.9 hours, p=0.004). While the difference in resolution time between groups was small, the authors suggested that "*consistent implementation of interventions that deliver small improvements in outcomes...can translate into substantial improvements in population health and health system function.*" However, this study was single-centred, non-blinded, and was a post-hoc subgroup analysis of completed trials (i.e. SMART and SALT-ED) and power was not prospectively calculated. Other studies on this topic have been limited due to small sample sizes (45-77 patients) leading to low power with limited conclusions.

## **STUDY OBJECTIVE(S); INCLUDING SPECIFIC AIMS AND/OR HYPOTHESES**

We hypothesize that patients who are administered IV RL will have faster DKA resolution without a concomitant increase in adverse outcomes when compared with normal saline. However, a pilot randomized controlled trial (RCT) is necessary to assess the feasibility of a future multi-centre trial. Our specific objectives for this pilot study are to determine the feasibility of conducting a full-scale multi-centred RCT and to use this pilot data to inform the future trial.

## **METHODS**

### ***Design and Setting***

This will be a single-centre, triple-blind pilot RCT evaluating the superiority of IV RL (intervention) compared to saline (comparator) in treating adult ED patients presenting with DKA over a one-year period. The study setting is London Health Sciences Centre (LHSC)'s Victoria Campus, an academic tertiary care centre with ~90,000 ED visits/year in London, Ontario. Study conduct will be in accordance with the CONSORT statement for pilot feasibility trials.

### ***Study Population – Inclusion/Exclusion Criteria***

There are no definitive criteria for diagnosing DKA. Thus, using the criteria employed by Self et al. and the Diabetes Canada guidelines we will include ED patients  $\geq 18$  years with a clinical diagnosis and laboratory values consistent with DKA, including:

- plasma glucose concentration  $\geq 14$  mmol/L
- plasma bicarbonate concentration  $\leq 18$  mmol/L and/or blood pH  $\leq 7.30$
- calculated anion gap  $> 10$  mmol/L
- presence of ketones/beta-hydroxybutyrate in serum and/or urine

We will exclude patients who:

- Are initially seen at another ED and transferred to LHSC for care and/or admission
- Receive  $> 1$  L of IV fluid prior to enrolment (e.g. pre-hospital by EMS or while waiting to be seen) – this may cause study contamination
- Are initially enrolled due to clinical suspicion of DKA based on elevated point-of-care glucose, but ultimately do not meet clinical/laboratory criteria for DKA (e.g. “hyperglycemia” only)
- Have euglycemic DKA (generally those on SGLT-2 inhibitors)

### ***Study Procedures***

#### **Screening, Consent, and Enrolment**

During weekday business hours (M-F 0700-1700), research assistants (RAs) will screen and identify eligible patients using our ED tracking board. They will approach the treating physician to confirm eligibility before discussing the study with the patient and seeking informed consent. Because the diagnosis of DKA requires laboratory confirmation, all patients with a point-of-care blood glucose confirming hyperglycemia ( $\geq 14$  mmol/L) will be approached for enrolment as a “possible DKA patient”. If the treating physician agrees that DKA is possible and IV fluid is indicated, study fluid will be administered per the randomization protocol after consent is obtained. If patients are initially enrolled but the physician ultimately confirms they do not meet DKA criteria, they will be excluded from the analysis. During evening and weekend hours, RAs

will be available on-call, however nighttime coverage (after 2300h) will not be feasible for this pilot. After hours (and in the event our processes are affected by a prolonged COVID-19 pandemic), treating physicians can directly enroll patients as there will be study posters to outline enrolment processes and physicians will receive email and in-person reminders on study recruitment. We will review daily ED visit logs to identify missed patients to screen for bias.

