### **Randomization, Blinding, Allocation Concealment**

Enrolled patients will be block randomized to treatment or comparator in a 1:1 allocation ratio. The block size will be unknown to investigators and those involved in patient care and will be small enough to ensure balance between each arm throughout the trial. The randomization list will be prepared by our pharmacy. The patients, treating physicians, and outcome assessors will be blinded to assigned treatment. Our pharmacy will prepare an opaque covering over each fluid bag within study kits, which will not be removed during the infusion to maintain blinding. Each bag will be labelled with a kit number and scannable bar code to ensure the patient receives study fluid as ordered which will be entered on their Medication Administration Record (Figure 1).

**Figure 1.** Image of Blinded Fluid Bag from Pharmacy

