### ***Study Outcomes***

#### **Primary Feasibility Outcome**

The primary feasibility outcome is patient recruitment rate over the one-year study period. We will also measure adherence to the protocol for this pilot study. This pilot is not powered to determine differences in treatment groups; however, a priori outcome definition and accurate outcome assessment is needed to inform the future study.

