#### **Efficacy Outcomes**

We also have efficacy outcomes consistent with those used by the previous study by Self et al.:

**Primary outcome:** time to DKA resolution (hours), defined as the time elapsed between ED presentation and ketoacidosis resolution, following criteria from the American Diabetes Association Consensus Statement on Hyperglycemic Crises (plasma glucose <11.1 mmol/L and two of: plasma bicarbonate ≥15mmol/L, venous pH >7.3 or anion gap ≤12mmol/L).

\*Of note, Diabetes Canada's guidelines lack definitive criteria for DKA resolution, only stating that insulin infusion should continue until ketosis resolves (measured by "normalization of plasma anion gap"). Following Self et al., patients discharged prior to evidence of laboratory criteria for DKA resolution will be classified as having DKA resolution at time of discharge.

**Secondary outcomes:** time to insulin infusion discontinuation (hours), intensive care unit admission, in-hospital death, hospital length of stay (days), hyper- or hypokalemia (>6.0 or <3.0 mmol/L) post-ED, in-hospital acute kidney injury post-ED (Stage 2 or greater – defined as serum creatinine increase >200% from baseline or <0.5mL/kg/hr urine output for <12 hours) and major adverse kidney events within 30 days, defined as a composite of: i) death, ii) new renal replacement therapy, or iii) final serum creatinine ≥200% baseline at the earliest of hospital discharge or 30 days after ED presentation).

Our hospital's DKA protocol involves hourly point-of-care glucose checks and bloodwork (electrolytes, including anion gap, and venous blood gas) every two hours while receiving insulin infusions. Patient characteristics and clinical/laboratory data will be collected via our electronic medical record. All outcomes listed above can be ascertained via health records review, which will occur at 1,3,7, and 30 days post-enrolment.

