## **DATA ANALYSIS**

We will follow an intention-to-treat analysis. Descriptive statistics will be used to summarize patient characteristics. Chi-square tests with 95% confidence intervals will be used to examine differences in categorical variables between groups, and two-tailed unpaired t-tests will be used to compare continuous variables. For this pilot study, we have not planned an interim analysis, Data Safety Monitoring Board, or adjudication committee, but these will be developed for the full-scale trial. This trial will be registered with ClinicalTrials.gov.

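### Randomised patients given study fluid are dropped if DKA is not confirmed, so the analysis as written is not the stated intention-to-treat, and no pre-fluid sample decides who is dropped

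*Combined protocol and SAP*

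**What the plan says.** Four parts of the combined protocol and SAP bear on this.

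- **Treatment starts before diagnosis.** Under Screening, Consent, and Enrolment, a point-of-care glucose of at least 14 mmol/L is enough to be approached. Then: "If the treating physician agrees that DKA is possible and IV fluid is indicated, study fluid will be administered per the randomization protocol". The Randomization section allocates enrolled patients 1:1.
- **Unconfirmed patients are removed afterwards.** The same enrolment section says: "If patients are initially enrolled but the physician ultimately confirms they do not meet DKA criteria, they will be excluded from the analysis". The exclusion criteria repeat the rule for patients enrolled on suspicion "but ultimately do not meet clinical/laboratory criteria for DKA". Neither place gives a time point or a sample.
- **The analysis is described differently.** The Data Analysis section says "We will follow an intention-to-treat analysis", with no exception and no modified set.
- **The decision is blinded.** The Randomization section says: "The patients, treating physicians, and outcome assessors will be blinded to assigned treatment".

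The secondary outcomes under Efficacy Outcomes include "in-hospital death, hospital length of stay (days), hyper- or hypokalemia (>6.0 or <3.0 mmol/L) post-ED, in-hospital acute kidney injury post-ED", plus a 30-day composite kidney endpoint that also counts death.

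**The concern.** An intention-to-treat set contains everyone randomised, analysed by assigned arm. A set that removes randomised patients, some of them already treated, on a finding made after randomisation is something else. An analyst cannot follow the enrolment section and the Data Analysis section together.

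Three consequences follow.

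1. **Membership may depend on treatment.** Without a named sample, a patient may be kept or dropped on blood taken after study fluid began. The Background says saline "can cause a hyperchloremic metabolic acidosis, particularly when administered in large volumes". Bicarbonate and pH are entry criteria, so the assigned fluid can move values that decide who is analysed. Blinding the physician does not prevent this, because the effect would be in the blood result and not in the judgement.
2. **Exposed patients leave the safety-type outcomes.** Someone who received study fluid and then had a potassium disturbance or kidney injury is not counted if DKA was not confirmed.
3. **Counts are left open.** The plan does not say that these exclusions will be reported by arm or kept apart from attrition. The full-scale sample size section says the pilot's attrition rate will feed the next calculation.

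**Working it through.** **Step 1. Can a randomised, treated patient be dropped?** The order in the text is: glucose of 14 mmol/L or more, physician agrees DKA is possible, consent, randomised fluid, later confirmation or not. Laboratory confirmation is not a condition for starting fluid. So yes.

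**Step 2. Does the Data Analysis section allow for it?** It gives one unqualified sentence and defines no other set. The exclusion rule and the label cannot both hold.

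**Step 3. Is a deciding sample named?** The inclusion criteria give thresholds: glucose ≥14, bicarbonate ≤18 and/or pH ≤7.30, anion gap >10, and ketones present. Efficacy Outcomes describes bloodwork every two hours during insulin infusion. No section links the eligibility decision to a particular draw, so post-fluid results will exist and are not ruled out.

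**Step 4. How could arm matter?** Bicarbonate or pH alone can satisfy the acidosis criterion. Arm can therefore change the result only for a patient who is not clearly past either cut-off and is close to at least one. Such a patient could meet the criterion after saline but not after Ringer's lactate. The anion gap, ketone, glucose and clinical criteria must also be met, and the documents claim no fluid effect on anion gap or ketones. The route is real but narrow. No input in the documents allows its size to be calculated.

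**Step 5. The plan's own counts.**
- Approached: 0.80 × 130 = 104.
- Recruited: 0.50 × 104 = 52.
- Minimum: 43/104 = 0.4135.
- Exact (Clopper-Pearson) 90% interval for 52/104: 0.4154 to 0.5846, which reproduces the stated 0.415 to 0.585.

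The 130 are visits coded as DKA, and the 104 are described as eligible patients. So 52 and 43 most naturally mean patients with DKA, although the text does not say so.

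**Step 6. How many patients might be dropped?** The share not confirmed, u, is not given. As an assumption only, if 52 means confirmed patients, the number to randomise is 52/(1 − u), rounded up:

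| Assumed u | Randomised | Dropped after randomisation |
|---|---|---|
| 5% | 55 | 3 |
| 10% | 58 | 6 |
| 20% | 65 | 13 |
| 30% | 75 | 23 |

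This shows how many randomised patients would go unreported under the current wording. It is not an estimate of bias.

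**The case against.** The strongest defence is that the exclusion is sensible, is stated in advance in two places and is applied by a blinded physician. Time to DKA resolution has no meaning in a patient who never had DKA. The stated example is hyperglycemia alone, which is far from borderline. The Background ties the acidosis concern particularly to large volumes. The pilot's main result is recruitment: "The primary feasibility outcome is patient recruitment rate over the one-year study period". It is not powered to compare arms. The Design section also commits to CONSORT reporting for pilot trials.

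Most of this stands, and it limits the severity. It supports a modified intention-to-treat set, but not the unqualified label or the silence on which sample decides. The content of the CONSORT statement is not in the documents, so it cannot be relied on to settle reporting by arm. As to attrition, the plan justifies its 10% as loss to follow-up, and nothing says unconfirmed patients would be added to it. Keeping them separate is a precaution and does not correct a stated error.

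A reader might go further and infer that one exclusion defeats the feasibility criterion, since 51/104 has an exact lower limit of 0.406 and 51/103 has 0.410, both below 0.413. The documents do not support that reading. The target is a minimum count of 43, and 51 exceeds it by 8. From 52, nine patients would have to be lost just to reach 43, which still meets it. The interval is a planning statement around the anticipated rate, and recruiting one patient fewer for any reason gives 51/104. The derivation from coded DKA visits also points to 52 confirmed patients, in which case the limit stays at 0.415.

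**Conclusion.** Wrong as written, of modest severity. The conflict between the exclusion rule and the intention-to-treat statement is on the face of the text and needs no assumption. So is the absence of a named deciding sample, and so is the loss of treated patients from the potassium, kidney and death outcomes.

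That retention could depend on arm rests on two conditions: that post-fluid blood is used for some patients, and that saline shifts bicarbonate or pH enough to cross a cut-off. Any effect is confined to a few borderline patients and is probably small. The documents give no basis for inferring that physicians would select patients by allocation.

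The recruitment counts need a definition, but the feasibility conclusion is not shown to fail.

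**What to change.** Reconcile the exclusion criteria, the enrolment section and the Data Analysis section, as follows.

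1. Call the efficacy set modified intention-to-treat.
2. For analysis-set membership only, have the blinded treating physician's exclusion decision rest on the first laboratory sample drawn before study fluid, for glucose, bicarbonate, pH and anion gap. Ketones may come from a later sample.
3. Where there is no pre-fluid sample, use the first available one, flag the patient, and repeat the analysis without flagged patients.
4. Report non-confirmed exclusions by arm and separately from attrition.
5. Summarise the potassium, kidney and death outcomes in everyone who received study fluid, by assigned arm. No time-to-resolution analysis is needed in patients who never had DKA.
6. State that 52 and 43 count DKA-confirmed patients, as the derivation implies, or define them otherwise.

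The cost is mainly wording, because the Data Collection section already abstracts data for each enrolled patient. There are two limits. Fluid can start on a point-of-care glucose, so a pre-fluid sample is not guaranteed and the fallback may be used often, which is why the repeat analysis is needed. A few patients whose acidosis appears only on later bloods will also leave the efficacy set.

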### **Intervention and Comparator**

The intervention is administration of IV Ringer's lactate and the comparator is administration of IV normal saline. Rate of study fluid will be at the treating physician's (both ED and inpatient, if consulted for admission) discretion. Apart from fluid administered, there will be no other changes to the patient's clinical care, and patients will receive standard DKA treatment which may include insulin, electrolyte replacement, and/or supportive management. Pharmacy-prepared kits of 8 x 1L bags of study fluid (in Self et al., a maximum of 7090mL was given) will be kept in a secure space within the ED. Once packaged, IV bags are useable for 30 days before expiration. If a kit is opened but not used completely, individual 1L bags may be returned to the pharmacy to save on costs.

### **Randomization, Blinding, Allocation Concealment**

Enrolled patients will be block randomized to treatment or comparator in a 1:1 allocation ratio. The block size will be unknown to investigators and those involved in patient care and will be small enough to ensure balance between each arm throughout the trial. The randomization list will be prepared by our pharmacy. The patients, treating physicians, and outcome assessors will be blinded to assigned treatment. Our pharmacy will prepare an opaque covering over each fluid bag within study kits, which will not be removed during the infusion to maintain blinding. Each bag will be labelled with a kit number and scannable bar code to ensure the patient receives study fluid as ordered which will be entered on their Medication Administration Record (Figure 1).

**Figure 1.** Image of Blinded Fluid Bag from Pharmacy

### ***Study Outcomes***

#### **Primary Feasibility Outcome**

The primary feasibility outcome is patient recruitment rate over the one-year study period. We will also measure adherence to the protocol for this pilot study. This pilot is not powered to determine differences in treatment groups; however, a priori outcome definition and accurate outcome assessment is needed to inform the future study.

#### **Efficacy Outcomes**

We also have efficacy outcomes consistent with those used by the previous study by Self et al.:

**Primary outcome:** time to DKA resolution (hours), defined as the time elapsed between ED presentation and ketoacidosis resolution, following criteria from the American Diabetes Association Consensus Statement on Hyperglycemic Crises (plasma glucose <11.1 mmol/L and two of: plasma bicarbonate ≥15mmol/L, venous pH >7.3 or anion gap ≤12mmol/L).

\*Of note, Diabetes Canada's guidelines lack definitive criteria for DKA resolution, only stating that insulin infusion should continue until ketosis resolves (measured by "normalization of plasma anion gap"). Following Self et al., patients discharged prior to evidence of laboratory criteria for DKA resolution will be classified as having DKA resolution at time of discharge.

**Secondary outcomes:** time to insulin infusion discontinuation (hours), intensive care unit admission, in-hospital death, hospital length of stay (days), hyper- or hypokalemia (>6.0 or <3.0 mmol/L) post-ED, in-hospital acute kidney injury post-ED (Stage 2 or greater – defined as serum creatinine increase >200% from baseline or <0.5mL/kg/hr urine output for <12 hours) and major adverse kidney events within 30 days, defined as a composite of: i) death, ii) new renal replacement therapy, or iii) final serum creatinine ≥200% baseline at the earliest of hospital discharge or 30 days after ED presentation).

Our hospital's DKA protocol involves hourly point-of-care glucose checks and bloodwork (electrolytes, including anion gap, and venous blood gas) every two hours while receiving insulin infusions. Patient characteristics and clinical/laboratory data will be collected via our electronic medical record. All outcomes listed above can be ascertained via health records review, which will occur at 1,3,7, and 30 days post-enrolment.

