#### ***Sample size for Full-Scale Trial***

The sample size calculation for this trial was based on a study of Clinical Effects of Balanced Crystalloids vs Saline in Adults with Diabetic Ketoacidosis which compared the clinical effects of balanced crystalloids with the clinical effects of saline for the acute treatment in DKA in two clinical trials (Isotonic Solutions and Major Adverse Renal Events Trial [SMART] and the

Saline Against Lactated Ringer's or Plasma-Lyte in the Emergency Department [SALT-ED]10). The primary outcome for this comparison was the time between ED presentation and DKA resolution, measured in hours. Self et al. (2020) found an absolute reduction in time to DKA resolution of 3.9 hours. In the balanced crystalloids group (n=94), the median time to resolution of DKA was 13.0 hrs [IQR: 9.5-18.8], while in the saline group (n=78) the median time to resolution was 16.9 hrs [IQR: 11.9-34.5]. The IQR was used to calculate the standard deviation for each group based on the following assumption for normally distributed data:  $SD=IQR/1.35$ . The pooled standard deviation was then calculated based on the sample size and standard deviation of each group from the Self et al. (2020) study [ $\sqrt{((n1-1)*SD1^2 + (n2-1)*SD2^2)/(n1+n2-2)}$ ] and was determined to be 12.37. To establish superiority of balanced crystalloids versus saline in the time to resolution of DKA, a superiority margin for a clinically significant difference was chosen to be a 40% (=6.76 hours) reduction in time to resolution of DKA based on expert consensus and patient partner feedback. A conservative attrition rate of 10% was selected for the sample size calculation, as loss to follow-up rates should be low given the nature of the intervention (IV fluids) and follow-up period (<24 hours). The actual attrition rate determined by this pilot study will inform the sample size calculation for the full-scale multicentre study. Therefore, to achieve 80% power at the 5% level of significance with equal allocation, the sample size for the balanced crystalloids (Ringer's lactate) group and the saline group, while accounting for a 10% loss to follow up and a 25% reduction in time to DKA resolution, is 516 participants (258 per group). The sample size was calculated using Wang and Ji's (2020) method for common clinical study designs available at <http://riskcalc.org:3838/samplesize/>.

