## **RISKS**

Participation in this study is entirely voluntary. Patients may refuse to participate, refuse to answer any questions, or withdraw from the study at any time with no effect on their future care. Participants do not waive any legal rights by signing the consent form. They will receive a copy of the letter of information should they be willing to consent.

There are no anticipated risks to participating in this study, other than a low possibility of a privacy breach occurring with the data collected during this study. However, the study team will take all necessary precautions to prevent this from happening and will remove any personal identifiers from all data collection forms.

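### Discharge before laboratory resolution counts as resolution whatever the reason for leaving, so an unresolved departure against advice gets an early resolution time that nobody observed

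*Combined protocol and SAP*

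**What the plan says.** The primary efficacy outcome in the Efficacy Outcomes section is "time to DKA resolution (hours), defined as the time elapsed between ED presentation and ketoacidosis resolution". Resolution is a laboratory state: "plasma glucose <11.1 mmol/L and two of: plasma bicarbonate ≥15mmol/L, venous pH >7.3 or anion gap ≤12mmol/L". The section then adds, following the earlier study of balanced crystalloids, that "patients discharged prior to evidence of laboratory criteria for DKA resolution will be classified as having DKA resolution at time of discharge".

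The word 'discharged' is not defined, and no section divides discharges by reason. The only mention of movement between hospitals is an exclusion for incoming patients: "Are initially seen at another ED and transferred to LHSC for care and/or admission". Transfer out is not mentioned.

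The Data Analysis section says "We will follow an intention-to-treat analysis" and that "two-tailed unpaired t-tests will be used to compare continuous variables". It plans no censoring and no sensitivity analysis for times assigned at discharge. The Data Collection section already lists discharge information among the items taken from the record.

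**The concern.** The outcome is measured in hours and shorter is better. When a physician sends a patient home as well, the hour of discharge is a defensible stand-in for a missing laboratory result. When a patient leaves against advice with ketoacidosis still present, departure shows only that resolution had not been seen by then. The rule treats both alike. For the second patient it replaces an unknown later time with a known earlier one, and the sooner the patient goes, the better the recorded result.

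The efficacy comparison and the pilot's picture of resolution times are both at stake. An arm with more unresolved departures looks faster than it was. If departures are equally common in both arms, a real difference is diluted. The number of patients whose resolution was never seen is also hidden among the observed times. The Primary Feasibility Outcome section says the efficacy outcomes are defined in advance and assessed accurately so that they can inform the next study, so the definition matters even though the pilot is not powered for efficacy.

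**Working it through.** The rule itself carries no figure to reproduce, so the check has two parts: what the text covers, and how far one affected patient moves the result.

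**Coverage of the text**

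- Physician-directed discharge before laboratory resolution: scored as resolved at discharge.
- Discharge against advice before laboratory resolution: scored the same way, because no exception is made.
- Transfer out before laboratory resolution: scored the same way only if transfer counts as discharge, which the documents do not settle.
- Withdrawal from the study: not covered by this sentence.

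**Inputs for the illustration**

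- 26 patients per arm (Sample Size).
- Saline group of the earlier study: median 16.9 h, quartiles 11.9 and 34.5 h; balanced-crystalloid group: median 13.0 h, quartiles 9.5 and 18.8 h; difference 3.9 h (Sample size for Full-Scale Trial).
- Departure hour: assumed, 4 h, with 8 h as an alternative.
- True resolution time of the patient who left: assumed, 16.9 h or 34.5 h.

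**Shift in the arm mean from one patient** = (true time − departure time) / 26

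- Leaves at 4 h, true time 16.9 h: 12.9 / 26 = 0.50 h
- Leaves at 4 h, true time 34.5 h: 30.5 / 26 = 1.17 h
- Leaves at 8 h, true time 16.9 h: 8.9 / 26 = 0.34 h
- Leaves at 8 h, true time 34.5 h: 26.5 / 26 = 1.02 h

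Across these cases one patient moves the arm mean by 0.34 to 1.17 h, which is 9% to 30% of 3.9 h. That comparison gives scale only, since 3.9 h is a difference in medians and the shift is in a mean.

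**Scale against sampling error**

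The plan's SD reproduces: 9.3/1.35 = 6.89, 22.6/1.35 = 16.74, and √[(93 × 6.89² + 77 × 16.74²)/170] = 12.37 h. The standard error of a difference in means at 26 per arm is 12.37 × √(2/26) = 3.43 h. One patient's shift of 0.50 to 1.17 h is therefore 0.15 to 0.34 of a standard error.

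**Equal departure rates in both arms**

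Fit a lognormal to each quoted median and quartile pair: log-SD = ln(18.8/9.5)/1.349 = 0.506 and ln(34.5/11.9)/1.349 = 0.789. If a fraction f leaves unresolved at an hour below the median, the recorded median sits where the true distribution function equals (0.5 − f)/(1 − f).

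- f = 5%: 0.45/0.95 = 0.474, z = −0.066. Medians become 16.9 × e^(−0.066 × 0.789) = 16.0 h and 13.0 × e^(−0.066 × 0.506) = 12.6 h. The difference is about 3.5 h.
- f = 10%: 0.40/0.90 = 0.444, z = −0.140. Medians become 15.1 h and 12.1 h. The difference is about 3.0 h.

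The 5% and 10% rates are assumptions, as is the lognormal shape.

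**The case against.** The rule is deliberate and disclosed. It copies the study that supplies the planning medians and SD, so it keeps the pilot comparable with its source. Patients, physicians and outcome assessors are blinded, and nothing in the documents predicts more unresolved departures in one arm than the other beyond chance or a real effect of treatment. The pilot's primary outcome is recruitment, and the only pilot result named as an input to the later sample size is attrition. All of this stands. It limits the size of the point, but it does not make an unobserved resolution observed. Comparability can be kept by showing both rules.

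A reader might infer more than the documents support:

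- **That transfers out are certainly scored as successes.** This depends on how the undefined word 'discharged' is read. The eligibility criteria use a separate word for movement between hospitals.
- **That withdrawals are scored as resolved.** The Risks section lets patients "withdraw from the study at any time with no effect on their future care", but leaving the study is not leaving hospital, and the discharge rule does not apply to it.
- **That the rule makes measured attrition close to zero by construction.** The plan says that "The actual attrition rate determined by this pilot study will inform the sample size calculation for the full-scale multicentre study". The discharge rule fills in a time only for patients discharged alive who stay in the study; withdrawals can still be counted.
- **That a false treatment difference should be expected.** A two-patient imbalance under the 4 h assumption would give 2 × 0.50 = 0.99 h (before rounding) to 2 × 1.17 = 2.35 h, but both the imbalance and the departure hour are assumed. Equal rates give dilution, not a false benefit.

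**Conclusion.** The point holds as a defect in the outcome definition. As written, the rule gives an early resolution time to a patient discharged against advice while still ketoacidotic, and no other section limits it. Transfer out is affected only if it counts as discharge.

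The effect in this trial cannot be stated because no departure rate is given. On the stated assumptions (26 per arm, departure at 4 h), one such patient lowers the arm mean by 0.50 to 1.17 h, well under one standard error of the pilot's comparison. It concerns the primary efficacy outcome that is to inform the full-scale trial. It leaves the recruitment result untouched and does not show that the arms will be biased in either direction. It should be corrected before enrolment, because the change is small and the definition is likely to be carried into the larger trial.

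**What to change.** 1. **Efficacy Outcomes.** Limit the rule to physician-directed discharge. Classify departures against advice and transfers out before laboratory resolution as 'resolution not observed'.
2. **Data Collection.** Record discharge disposition as a specific field, taken from the discharge information already abstracted.
3. **Reporting.** Give, by arm, the number of times that were laboratory-confirmed, assigned at physician-directed discharge, and not observed. Use only the not-observed count as non-ascertainment of this outcome for planning; discharge-assigned times have been accepted as resolution and should not be counted again as missing.
4. **Data Analysis.** The unpaired t-test cannot use censored times, so add a time-to-event analysis from ED presentation, with not-observed patients censored at their last laboratory sample. State that this censoring may be informative, since leaving while unresolved may be related to prognosis. Show the result under the earlier study's rule beside it for comparability.

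Cost: revised wording in the outcome and analysis sections, one abstraction field, one extra analysis, and a few patients with censored times.
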